### **Post-Treatment Follow-Up Period**

During the 12-Month Post-Treatment Follow-Up Period, visits will occur either by phone or on-site from Months 1 through 12.

During the Phone Visits (Post-Treatment Follow-up Visits Month 2, Month 4, Month 5, Month 7, Month 8, Month 10 and Month 11), Site Personnel will discuss adverse events, concomitant medications, if applicable, obtain the results of the subject's self-administered urine pregnancy test and will remind subjects of the importance of consistent use of appropriate and effective dual non-hormonal contraception throughout the Post-Treatment Follow-Up Period. Subjects may begin taking hormonal contraceptive preparations only after completing the Post-Treatment Follow-Up Month 2 Visit and following the return to a full menses (menses with full menstrual flow) in the Post-Treatment Follow-Up Period. If the subject's full menses has not returned by the Post-Treatment Follow-Up Month 2 Visit, an adverse event of amenorrhea should be documented.

Subjects will be required to collect sanitary products for their first menses with full menstrual flow in the Post-Treatment Follow-Up Period. If the subject does not return sanitary products for her first full menses, she will be required to collect and return sanitary products for her next full menses. Subjects will return the sanitary products at a Product Collection Visit within approximately 5 days after cessation of bleeding or spotting. The Post-Treatment UBQ will be administered by Site Staff at each Phone or Site Visit until the subject has returned sanitary products from her first full menses in the Post-Treatment Follow-Up Period. Once a subject returns sanitary products from a full menses in the Post-Treatment Follow-Up Period, the Post-Treatment UBQ no longer needs to be completed.

All subjects will be required to have DXA scans at Post-Treatment Follow-Up Months 6 and 12.

Procedures and assessments in the Post-Treatment Follow-Up Period should be performed as specified in [Appendix C](#), Study Activities.

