#### **5.2.2.4 Prohibited Therapy**

All hormonal forms of birth control (except the emergency contraceptive pill, levonorgestrel 1.5 mg [such as Plan B®], or ulipristal acetate 30 mg [such as Ella® or

EllaOne®) are prohibited during the Treatment Period and until the Post-Treatment Follow-Up Month 2 Visit and return to first full menses. If subject does not return to menses she must continue use of dual non-hormonal contraception.

For subjects who are prescribed/administered the emergency contraceptive pill during the study, the AbbVie TA MD must be informed.

Tranexamic acid should not be taken during the Treatment or Post-Treatment Follow-Up Period; however, tranexamic acid, if necessary, can be prescribed following completion of the Post-Treatment Follow-Up Month 2 Visit and the subject has returned to first full menses.

Due to the extensive list of herbal remedies and supplements, please contact the AbbVie TA MD for any that may be prohibited. Generally-speaking, any supplements or herbal remedies used to treat premenstrual or gynecological problems, such as black cohosh, are excluded.

The following medications should not be taken during the Treatment and Post-Treatment Follow-Up Period.

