**Table 2. Prohibited Medications (Continued)**

Prohibited During the Treatment Period and Post-Treatment Follow-Up Periods	
Bisphosphonates, RANKL inhibitors, Anabolic Bone Agents or rPTH, such as:	Fosamax ® , Fosamax Plus D ® , Binosto ® , Boniva ® , Reclast ® , Zomata ® , Prolia ® , XGEVA, Forteo ® , Actonel ® , Atelvia ® , Miacalcin ® , Fortical ®
Synthetic Prostaglandin E1 (PGE1) Analogs, such as:	Misoprostol (Cytotec ® , Arthrotec ® ) Single use of PGE1 for cervical preparation prior to biopsy is allowed; chronic use is prohibited
Oral Retinoids (topical applications are permitted), such as:	Accutane ® (isotretinoin)

- \* E2/NETA will be taken by subjects randomized to the E2/NETA dose group.
- # Due to the extensive list of herbal remedies and supplements, please contact the AbbVie TA MD for any that may be prohibited.
- % Subjects may begin the use of hormonal contraceptives or tranexamic following completion of the Post-Treatment Follow-Up Month 2 Visit and she has returned to first full menses. Tranexamic acid, if necessary can be prescribed following completion of the Post-Treatment Follow-Up Month 2 Visit and return to first full menses.

If a prohibited medication is necessary to treat an adverse event or a pre-existing condition other than uterine fibroids, the AbbVie TA MD noted in Section 6.1.5 should be consulted; however, if clinically required and to prevent an immediate hazard to the subject being treated, the AbbVie TA MD should be notified as soon as possible after the start of use. Additionally, if a subject takes a prohibited medication during the study, except as permitted per protocol (hormonal medication taken after completion of the Post-Treatment Follow-Up Month 2 Visit and return to first full menses), her continued participation in the study will be evaluated by the Investigator and the AbbVie TA MD. If there are any questions regarding prior or concomitant therapy, please contact your Study Monitor.

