### **5.2.3 Contraception Recommendations and Pregnancy Testing**

#### **Contraception Counseling/Dispense Contraceptives**

Subjects (excluding those subjects who have had a bilateral tubal ligation or bilateral tubal occlusion) will continue to be counseled at every visit throughout their participation in the study on the importance of pregnancy prevention and the use of appropriate and effective

methods of birth control during the Treatment and Post-Treatment Follow-Up Periods of the Extension Study.

Subjects must agree to use two forms of non-hormonal contraception (dual contraception) consistently throughout the Treatment Period and Post-Treatment Follow-Up Periods (Subjects may begin the use of hormonal contraception (e.g., oral or IUD) after completing the Post-Treatment Follow-Up Month 2 Visit and have returned sanitary products for a full menses).

Acceptable methods of dual non-hormonal contraception include the following combinations:

- Condom with spermicide (foam, gel, or polymer film)
- Diaphragm with spermicide (condom may or may not be used)
- Cervical cap with spermicide (condom may or may not be used)

Subjects are not required to use dual contraception methods if:

- Sexual partner(s) is vasectomized at least 6 months prior to Screening
- Subject practices total abstinence from sexual intercourse, as the preferred lifestyle of the subject; periodic abstinence is not acceptable
- Subject had a bilateral tubal occlusion (including ligation and blockage methods such as Essure®) at least 4 months prior to Screening.
- Subject is not sexually active with men; periodic sexual relationship(s) with men requires the use of dual non-hormonal contraception as indicated above.

Subjects may begin the use of hormonal contraception in place of dual non-hormonal contraception during the Post-Treatment Follow-Up Period if they meet both of the following:

- Completed the Post-Treatment Follow-Up Month 2 Visit and
- Returned sanitary products for a full menses in the Post-Treatment Follow-Up Period

If subject does not return to full menses, she must continue use of dual non-hormonal contraception.

The following measures will be taken to help ensure pregnancy prevention during the Extension Study.

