### **5.4 Removal of Subjects from Therapy or Assessment**

Each subject has the right to withdraw from the study at any time. In addition, the Investigator may discontinue a subject from the study at any time if the Investigator considers it necessary for any reason, including the occurrence of an adverse event or noncompliance with the protocol. Subjects who withdraw from the study will not be replaced. Each subject will be withdrawn from the study if any of the following occur:

- The subject decides to withdraw consent for any reason.
- The investigator believes it is in the best interest of the subject.
- Clinically significant deterioration of the subject's medical status as determined by the investigator.
- The subject requires surgical intervention for treatment of uterine fibroids and menstrual bleeding or other procedures including hysterectomy, myomectomy, uterine artery embolization, high intensity focused ultrasound (HIFU), endometrial ablation, dilation and curettage (D&C), etc. during the Treatment Period. In the post treatment period these procedures do not warrant withdrawal if performed during the Post-Treatment Period unless a hysterectomy with bilateral salpingo-oophorectomy (BSO) is performed and the Subject does not plan to use Hormone Replacement Therapy within 1 month of the surgery date.
- The subject becomes pregnant.

- The subject has ALT or AST elevation > 5 times the upper limit of normal confirmed upon repeat during the Treatment Period.
- The subject's legally acceptable representative decides to withdraw consent for any reason (when applicable).
- Heavy menstrual bleeding during the Treatment Period that requires a blood transfusion at any time after having taken 28 days of study drug. If a subject has a blood transfusion during the Post-Treatment Period, the AbbVie TA MD should be contacted to determine if the subject can remain in the study.
- Any other medical reason that AbbVie or the study investigator deems appropriate.

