#### **5.4.1 Discontinuation of Individual Subjects**

In the event that a subject withdraws or is prematurely discontinued from study drug treatment, the subject should complete the Treatment Period Premature Discontinuation Visit as soon as possible (preferably within 2 days of last dose of study drug, if possible) and undergo study procedures as outlined in [Appendix C](#), Study Activities. Subjects who prematurely discontinue during the Treatment Period are expected to enter the 12-Month Post-Treatment Follow-Up Period, unless discontinuing due to pregnancy. Each subsequent monthly Post-Treatment Follow-Up Period Visit should be scheduled based on the date of the last dose of study drug.

In the event that a subject withdraws or is prematurely discontinued during the Post-Treatment Follow-Up Period, the subject should complete the Post-Treatment Premature Discontinuation Visit as soon as possible and undergo study procedures as outlined in [Appendix C](#), Study Activities. These procedures should not interfere with the initiation of any new treatments or therapeutic modalities the Investigator determines are necessary to treat the subject's condition. The reason(s) for the discontinuation from the study will be recorded in the eCRFs.

All used and unused study drug containers will be returned to the study site.

If a subject becomes pregnant during the Treatment or Post-Treatment Follow-Up Periods, no additional study procedures, except an ultrasound will be conducted. Refer to Section 6.1.6 for instructions on reporting of a pregnancy to the Sponsor and the required follow-up on the subject/fetus and live births.

If a subject is discontinued from the study with an ongoing adverse event or an unresolved laboratory result that is clinically significant (as determined by the Investigator), the Investigator will attempt to provide follow-up until a satisfactory clinical resolution of the laboratory result or adverse event is achieved.

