11.3.5 Fibroid and Uterine Volume, FIGO Classification, Adenomyosis, and Post-Treatment Menses

11.3.5.1 **Fibroid and Uterine Volume**

Fibroid and uterine volume data will be summarized as observed. Analyses will be conducted separately for results obtained from TAU/TVU and MRI.

The change and percent change in the volume of the largest (primary) fibroid, the total fibroid volume (3 largest fibroids), and the uterine volume from Baseline to Month 3 (if applicable) and Month 6 during the Treatment Period will be summarized for each analysis group. The change and percent change at Post-Treatment Month 3 and Post-Treatment Month 6 (if applicable) during the Post-Treatment Follow-up Period will also be summarized for each analysis group.

The number and percentage of subjects with $\geq 25\%$ reduction from Baseline in total fibroid volume at Month 3 (if applicable) and Month 6 each during the Treatment Period will be summarized for each analysis group. The same summary will be provided for largest (primary) fibroid volume and uterine volume, respectively.

FIGO Classification 11.3.5.2

The number and percentage of subjects with fibroids at each location (e.g., intramural, subserosal, submucosal non-pedunculated, and subserosal pedunculated) according to the FIGO classification³ will be summarized for each analysis group at Baseline, Month 3 (if

applicable) and Month 6 during the Treatment Period and Post-Treatment Month 3 and Post-Treatment Month 6 (if applicable) during the Post-Treatment Follow-up Period.

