12.4.2 BMD in the Post-Treatment Follow-Up Period

Percent change from Baseline to Post-Treatment Follow-up Month 6, Post-Treatment Follow-up Months 7 – 11, and Post-Treatment Follow-up Month 12 will be summarized for each analysis group with descriptive statistics. There will be no statistical testing of Post-Treatment Follow-up BMD values.

The analysis of percent change in BMD will be repeated to include only the subset of subjects who had a Treatment Month 6 and a Post-Treatment Follow-up Month 6 scan. Similarly, this analysis will be repeated to include only the subset of subjects who had a Treatment Month 6 and a Post-Treatment Follow-up Month 12 scan.

Percent change from Baseline in BMD to each of the Post-Treatment visits will be summarized for each analysis group with frequencies and percentage for categories of BMD decrease: $\leq 0\%$, $> 0\% - \leq 1.5\%$, $> 1.5\% - \leq 3\%$, $> 3\% - \leq 5\%$, > 5% - < 8%, and $\geq 8\%$.

Cross-tabulations of the number and percentage of subjects in each of the previously noted categories of percent change from Baseline for the following:

- Treatment Month 6 to Post-Treatment Follow-up Month 6
- Treatment Month 6 to Post-Treatment Follow-up Month 12
- Final Treatment to Post-Treatment Follow-up Month 6
- Final Treatment to Post-Treatment Follow-up Month 12
- Post-Treatment Follow-up Month 6 to Post-Treatment Follow-up Month 12.

The subjects included in these analyses will be limited to those who had values at these time points.

As described above for the Treatment Period, continuous and categorical summaries of the Z-score and T-score at each time point during the Post-Treatment Follow-up Period will be provided.

Listings of subjects meeting the following thresholds during the Post-Treatment Followup period will be provided:

- Listing of subjects with bone decrease \geq 3% and T-score < -1.0 in the same region
- Listing of subjects with T-score ≤ -1.5 .

For the purposes of assessing post-treatment BMD recovery, the following summaries will be provided. The "recovery" statistic will be defined as

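### Follow-up BMD recovery and fibroid volume summaries make no cut at new hormone use or fibroid procedures, so off-drug recovery cannot be separated from later treatment

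*SAP*

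**What the plan says.** **Who stays in follow-up.** Protocol 5.4 lists fibroid procedures (hysterectomy, myomectomy, embolization, HIFU, ablation and others) that require withdrawal during treatment, then adds: "In the post treatment period these procedures do not warrant withdrawal if performed during the Post-Treatment Period". The one exception is hysterectomy with BSO when the woman does not plan HRT within 1 month. Women who stop study drug early also come in, under Protocol 5.4.1: "Subjects who prematurely discontinue during the Treatment Period are expected to enter the 12-Month Post-Treatment Follow-Up Period, unless discontinuing due to pregnancy".

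**When new treatment may start.** Protocol 5.1 sets two conditions: "Subjects may begin taking hormonal contraceptive preparations only after completing the Post-Treatment Follow-Up Month 2 Visit and following the return to a full menses". Protocol 5.2.3 words the second one more strictly: "Returned sanitary products for a full menses in the Post-Treatment Follow-Up Period". For tranexamic acid, Protocol 5.2.2.4 says that it "can be prescribed following completion of the Post-Treatment Follow-Up Month 2 Visit and the subject has returned to first full menses".

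**Which data are summarised.**
- SAP 7.4.2 assigns BMD, ultrasound and MRI data to follow-up by days since last dose alone (more than 28).
- SAP 11.3.5.1: "Fibroid and uterine volume data will be summarized as observed". Change and percent change are reported at Post-Treatment Months 3 and 6.
- SAP 12.4.2 gives BMD percent change and then: "For the purposes of assessing post-treatment BMD recovery, the following summaries will be provided". The recovery statistic requires only that BMD was below baseline at the final treatment scan. SAP 12.1 bases all safety analyses on observed data.
- SAP 12.7.2 summarises endometrial thickness in follow-up, also without a cut.
- SAP 11.3.5.4 summarises first post-treatment menses for everyone who entered follow-up and for two subsets defined by Final Month bleeding.
- SAP 8.3 tabulates follow-up medications but does not link them to these analyses.

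**The concern.** Recovery of bone after treatment is a stated design aim (Protocol 5.1, SAP 4.2), and the SAP builds a dedicated statistic for it. A reader will take that statistic as what bone does once elagolix stops. A DXA taken months into hormonal contraception or HRT, or after oophorectomy, does not show that, yet it enters the same mean, categories and distribution plot. The volume tables have a parallel problem: a myomectomy or embolization changes the measured quantity directly, and the later scan still counts as change after elagolix. At stake is the interpretation of the post-treatment safety and durability tables, bone above all.

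**Working it through.** **1. The SAP's own example.** Recovery = 100 × (change to final − change to Month X) / (change to final). With −2% at end of treatment and −1% at Post-Treatment Month 6: 100 × ((−2) − (−1)) / (−2) = 50%. This reproduces the SAP figure.

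**2. Sensitivity of the ratio.** If the follow-up scan in that example reads −0.5% instead of −1%, recovery is 100 × ((−2) − (−0.5)) / (−2) = 75%. If it reads −1.5%, recovery is 25%. Half a percentage point of BMD moves the individual value by 25 points.

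**3. Possible hormone exposure before each visit.** A month is 28 days, so Month 2 is day 56 after last dose. Maximum permitted exposure = nominal day − 56.

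| Visit | Nominal day | Possible days on hormones | Share |
|---|---|---|---|
| Month 3 (volume) | 84 | 28 | 33% |
| Month 6 (volume, BMD) | 168 | 112 | 67% |
| Month 12 (BMD) | 336 | 280 | 83% |

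The BMD windows in SAP Table 7 do not remove this. Month 6 runs from after day 140 to day 196, which leaves room for 84 to 140 days of exposure. Month 12 starts after day 308, which leaves room for more than 252 days.

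**4. Does the full-menses condition hold many women back?** Protocol 3.2.2 reports, for Phase 2b women who were amenorrheic on entering follow-up, return to menses by Month 2 in 52% + 42% = 94% (Cohort 1) and 59% + 38% = 97% (Cohort 2). Those figures are for menses, not specifically full menses, but they suggest that the condition delays few women.

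**5. BMD mixing, assumed inputs.** Shift in group mean recovery = share on hormones × difference in recovery. Assume a share of 5% to 30% and a difference of 25 to 50 points, of either sign. The smallest shift is 0.05 × 25 = 1.25 points and the largest is 0.30 × 50 = 15 points, in either direction.

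**6. Volume mixing, assumed inputs.** Suppose 2% to 15% of women have a hysterectomy that is recorded as uterine volume 0 (−100%), and the others average −10% to −30%. The shift is share × (−100 − mean of the others). The smallest is 0.02 × (−100 + 30) = −1.4 points and the largest is 0.15 × (−100 + 10) = −13.5 points. If no volume is recorded after hysterectomy, those women drop out of the as-observed mean instead. The documents do not say which applies.

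**7. First menses.** Permitted hormones come after a full menses. SAP 11.3.5.4 counts the first menses, met by a single day of bleeding or spotting, so permitted hormones should not change its timing. A procedure before that menses can. A woman who has had a hysterectomy stays in the population, and SAP 11.3.5.4 gives no category or censoring rule for someone who never has the event.

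**The case against.** The case against has weight.

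- The summaries are descriptive. SAP 12.4.2 rules out testing of follow-up BMD, and an as-observed table is a legitimate description of what happens to women after stopping, whatever they do next. Medians, categories and a distribution plot also limit the influence of a few women. This stands, and it is why the as-observed tables should stay. It does not tell a reader how bone behaves off treatment.
- A reader might infer that hormones distort time to first menses. The documents do not support this, because the full-menses condition places permitted hormones after the event. A narrow route remains for bleeding volume. If products from the first full menses are not returned, the next full menses is collected (Protocol 5.1), and tranexamic acid may by then be permitted. Hormonal contraception may be too, under the wording that asks only for return of menses.
- A reader might infer that the SAP presents fibroid shrinkage as recovery or as persisting drug effect. It does not. Only BMD carries the recovery label, and the design aim names bone and general safety.
- A reader might infer a known direction, such as hidden regrowth. No source in the documents supports one.
- The Phase 2b spine contrast in Protocol 3.2.2 (−0.1% against −3.6%, so 3.5 points) compares add-back given with elagolix to elagolix alone. It does not measure the effect of contraception in women off drug with menses restored.
- Scope is limited. Ultrasound in follow-up is at Months 3 and 6 and MRI at Month 3, so later procedures cannot affect scheduled volume data. BSO without planned HRT leads to withdrawal, so few later scans are expected in those women.

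**Conclusion.** The gap is real in this form: the protocol permits new hormones and keeps most women after fibroid procedures, while SAP 7.4.2, 11.3.5.1 and 12.4.2 have no cut, flag or supportive analysis for either. It matters most for BMD, where up to two thirds of the time before the Month 6 scan and five sixths before Month 12 may be on permitted hormones. Fibroid and uterine volume come second, mainly through procedures other than hysterectomy. For first menses, the point is limited to procedures before that menses.

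Neither size nor direction can be computed. The ranges of 1.25 to 15 points of recovery and 1.4 to 13.5 points of uterine volume rest wholly on assumed rates and differences, and show only what mixing could do. The primary endpoint and the Treatment Period analyses are untouched. This is an inexpensive improvement to interpretability and does not challenge the trial's main conclusions.

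**What to change.** Keep every as-observed follow-up summary and add, beside it:

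1. **SAP 12.4.2:** BMD percent change and recovery using only scans before the first start of hormonal contraception or HRT, or oophorectomy.
2. **SAP 11.3.5.1 and 12.7.2:** fibroid and uterine volume and endometrial thickness using only measurements before the first uterine procedure in follow-up.
3. **All of these:** the number of women and scans excluded, per analysis group.
4. **SAP 11.3.5.4:** a separate count of women with a hysterectomy or other procedure before their first post-treatment menses.

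State in one sentence what each version describes: outcome whatever treatment follows, or outcome before any such treatment.

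Medication start and end dates are already required (Protocol 5.2.2.1). Procedure dates need confirming: the HCRU questionnaire covers the Treatment Period only, and the follow-up schedule in Protocol Appendix C has no row for procedures. The passages on when hormonal contraception may start (return of a full menses, or return of its products) should be reconciled, so that the cut-off date is applied consistently.

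The cost is SAP wording, date filters and a few tables. The added tables will hold fewer women and may be selective: if women with regrowth are those who have procedures, removing their later scans could understate regrowth. That is why the two versions must be shown together, with counts, and why neither should replace the other.
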